## **2.17. Protocol Adherence**

The study investigators are responsible for performing the study in compliance with the protocol. Non-adherence to the protocol is to be classified as a protocol violation or protocol deviation, as defined below.

### **Protocol Violation**

ZELTIQ P/N: [REDACTED]

Protocol Number: ZA17-005

This document and the contents hereof are considered proprietary and confidential information of ZELTIQ Aesthetics, Inc. Disclosure to unauthorized individuals or dissemination, publication or copying is prohibited without prior written consent of ZELTIQ.

Non-adherence to the protocol that may result in significant additional risk to the subject (e.g., enrollment of a subject who does not meet the study criteria). Or, non-adherence to Good Clinical Practices (GCP) that may impact patient safety (e.g., failure to obtain proper consent prior to performing study procedures). Violations should be reported to the study Sponsor within 5 working days and reported to the IRB per IRB guidelines.

#### Protocol Deviation

Non-adherence to study procedures which does not result in additional risk to the subject (e.g., subject missed visit). Protocol deviations are not required to be reported to the IRB; however, they must be recorded on the study case report forms and may be reported and reviewed in conjunction with the progress report as part of the annual review process.

### **2.18. Adverse Events**

Adverse events (AE) will be assessed continuously throughout the study. An AE is defined in accordance with ISO 14155 as any untoward medical occurrence, unintended disease or injury, or untoward clinical signs (including abnormal laboratory findings) in study participants, users, or other persons temporally associated with the use of study treatment, whether or not considered related to the study treatment.

Disease signs and symptoms that existed prior to the study treatment are not considered AEs unless the condition recurs after the patient has recovered from the pre-existing condition or the condition worsens in intensity or frequency during the study.

AEs will be monitored throughout the study beginning with signing of informed consent. At each post-baseline visit, the investigator will begin querying for AEs by asking each patient a general, non-directed question such as “Have you had any changes to your condition since your last visit?” Previous AEs and changes in therapy/concomitant medications are to be updated. Directed questioning and examination will then be done as appropriate. All reportable AEs and clinically significant abnormal laboratory findings will be documented on the appropriate CRF.

Adverse events will be reported by the participant (or, when appropriate, by a caregiver, surrogate, or the participant's legally authorized representative). The investigator and any designees are responsible for detecting, documenting, and recording events that meet the definition of an AE or SAE and remain responsible for following up AEs that are serious, considered related to the study treatment or study procedures, or that caused the participant to discontinue the study.

ZELTIQ P/N: [REDACTED]  
Protocol Number: ZA17-005

This document and the contents hereof are considered proprietary and confidential information of ZELTIQ Aesthetics, Inc. Disclosure to unauthorized individuals or dissemination, publication or copying is prohibited without prior written consent of ZELTIQ.

### **Adverse Device Effect (ADE)**

Any sign, symptom, or disease in a study subject that occurs during the course of a clinical trial that is determined by the Investigator to have a causal relationship or possible causal relationship with the device under investigation. This definition includes any AEs resulting from insufficient or inadequate instructions for use, deployment, implantation, installation, or operation, or any malfunction of the investigational medical device as well as any event resulting from use error (per ISO 62366) or from intentional misuse of the investigational medical device.

### **Serious Adverse Device Effect (SADE)**

A serious adverse device effect (SADE) is defined in accordance with ISO 14155 as “an adverse device effect that has resulted in any of the consequences characteristic of a serious adverse event.”

### **Unanticipated Serious Adverse Device Effect (USADE)**

An unanticipated serious adverse device effect (USADE) is defined in accordance with ISO 14155 as “any serious adverse device effect which by its nature, incidence, severity, or outcome has not been identified in the current version of the risk analysis report.” The investigator is to consult the IDFU for anticipated risks or anticipated AEs.

### **Device Deficiency**

A device deficiency is defined in accordance with ISO 14155 as “inadequacy of a medical device with respect to its identity, quality, durability, reliability, safety, or performance.” Device deficiencies include malfunctions, use errors, and inadequate labeling.

If a device deficiency occurs, the investigator will notify the Sponsor using the fax number or email on the front page of the protocol. Device deficiencies shall be documented throughout the study and appropriately managed by the Sponsor. The Sponsor shall review all device deficiencies and determine and document in writing whether they could have led to an SADE. These shall be reported to the regulatory authorities and IRBs/ECs as required by national regulations.

### **Serious Adverse Event (SAE)**

An SAE is defined in accordance with ISO 14155 as an AE that:

1. Led to death

ZELTIQ P/N: [REDACTED]

Protocol Number: ZA17-005

2. Led to serious deterioration in the health of the patient, that either resulted in:

- a. a life-threatening illness or injury, or
- b. a permanent impairment of a body structure or a body function, or
- c. inpatient or prolonged hospitalization, or
- d. medical or surgical intervention to prevent life-threatening illness or injury or permanent impairment to a body structure or a body function, or
- e. led to fetal distress, fetal death or a congenital abnormality or birth defect

NOTE: Planned hospitalization for a pre-existing condition, or a procedure required by the protocol, without serious deterioration in health, is not considered an SAE.

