### **Time Period and Frequency for Collecting AE and SAE Information**

All AEs and SAEs from the signing of the ICF until the last follow-up visit will be collected at the timepoints specified in the schedule of activities, and as observed or reported spontaneously by study participants.

Medical occurrences that begin after signing of informed consent and before administration of study treatment will be recorded as an AE on the appropriate CRF.

All SAEs will be recorded and reported to the sponsor or designee within 24 hours of learning about the report. All non-serious AEs related to the devices used in the study, as well as Device Complaints, will be reported to the sponsor within 7 working days. The investigator will submit any updates on these events to the sponsor within 24 hours of it being available.

Investigators are not obligated to actively seek AE or SAE in former study participants. However, if the investigator learns of any SAE, including a death, at any time after a participant has completed the final visit of the study, and he/she considers the event to be reasonably related to the study treatment or study participation, the investigator must promptly report the event to the sponsor.

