### Serious Adverse Event Reporting Procedures

All serious adverse events must be reported to the Sponsor within 1 working day of discovery or notification of the event and according to IEC/IRB requirements and the institution at which the study is conducted, if applicable. Serious adverse event information and any follow-up information will be recorded on a Serious Adverse Event Form and transmitted to the Sponsor using the contact information provided by the Sponsor. Note that for each drug/device used in this study, a separate SAE form and contact information will be used. The Sponsor will be responsible for evaluating and reporting any serious adverse events and suspected unexpected serious adverse reactions in accordance with all applicable laws and regulations.

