### **3.3. Investigator Responsibilities**

#### **3.3.1. General Responsibilities**

Investigators are responsible for ensuring the investigation is conducted according to all signed agreements, the Investigational Plan, and applicable FDA regulations. The investigator must protect the rights, safety, privacy and welfare of the subjects under the Investigator's care. Investigators will assume overall responsibility and accountability for study site staff and for the clinical data obtained during the study. The investigator assumes all responsibilities per 21 CFR 812, 21 CFR 312, and other applicable regulations, including but not limited to:

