This document and the contents hereof are considered proprietary and confidential information of ZELTIQ Aesthetics, Inc. Disclosure to unauthorized individuals or dissemination, publication or copying is prohibited without prior written consent of ZELTIQ.

Potential Adverse Effect	Description
Vasovagal Symptoms	The occurrence of symptoms of anxiety, lightheadedness, dizziness, nausea, sweating, near syncope, or syncope (fainting).
Motor Nerve Injury	Injury to the lower face motor nerves such as marginal mandibular nerve (lower lip weakness) or hypoglossal nerve (tongue deviation).
Xerostomia	Injury to the submandibular gland as evidenced by the subjective decrease in saliva production.
Contour Irregularity	Significant indentation or contour irregularity in the treatment area that would require surgical intervention.
Allergic/Irritant Contact Dermatitis	Itchy rashes and skin peeling that may result from prolonged exposure to gel or applicator pressure
Subcutaneous Induration	Hardness within the treatment area, either as general firmness or discrete nodules. May present with pain and/or discomfort.
Paradoxical Hyperplasia	Visibly enlarged tissue volume within the treatment area which may develop 2-5 months after treatment. Surgical intervention may be required.
Other	Any other untoward medical event determined by the investigator to be an adverse event, regardless of the relationship to the device or treatment.

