**KYBELLA®**

- KYBELLA® is contraindicated in the presence of infection at the injection sites.
- Marginal mandibular nerve injury  
Cases of marginal mandibular nerve injury, manifested as an asymmetric smile or facial muscle weakness (paresis), were reported during clinical trials. To avoid the potential for nerve injury, KYBELLA® should not be injected into or in close proximity to the marginal

mandibular branch of the facial nerve. All marginal mandibular nerve injuries reported from the trials resolved spontaneously (range 1-298 days, median 44 days).

- **Dysphagia**

Difficulty swallowing (dysphagia) occurred in clinical trials in the setting of administration site reactions, e.g., pain, swelling, and induration of the submental area. Cases of dysphagia spontaneously resolved (range 1-81 days, median 3 days). Subjects with current or prior history of dysphagia were excluded from clinical trials. Avoid use of KYBELL®A in these patients as current or prior history of dysphagia may exacerbate the condition.

- **Injection site hematoma/bruising**

In clinical trials, 72% of subjects treated with KYBELL®A experienced injection site hematoma/bruising.

KYBELL®A should be used with caution in patients with bleeding abnormalities or who are currently being treated with antiplatelet or anticoagulant therapy as excessive bleeding or bruising in the treatment area may occur.

- Risk of injecting in proximity to vulnerable anatomic structures. To avoid potential tissue damage, KYBELL®A should not be injected into or in close proximity (1-1.5 cm) to salivary glands, lymph nodes and muscles.
- Injection site alopecia: withhold subsequent treatments until resolution.
- Injection site ulceration and necrosis: do not administer to the affected area until complete resolution.

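### The protocol's one definition of seriousness has no criterion for prolonged but reversible harm, so a long KYBELLA nerve paresis can be classed non-serious and then has no fixed reporting deadline

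*Combined protocol and SAP*

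**What the plan says.** - **Definition.** Section 2.18, Serious Adverse Event (SAE), opens with "An SAE is defined in accordance with ISO 14155 as an AE that" and lists death, life-threatening illness or injury, "a permanent impairment of a body structure or a body function", hospitalization, "medical or surgical intervention to prevent life-threatening illness or injury or permanent impairment to a body structure or a body function", and fetal harm. The Pregnancy paragraph adds abnormal pregnancy outcomes. No separate definition is given for the drug.
- **Known KYBELLA harm.** Section 6.2 says that the marginal mandibular nerve injuries (asymmetric smile, facial weakness) in earlier trials all "resolved spontaneously (range 1-298 days, median 44 days").
- **Known CoolSculpting harms.** Section 6.2 also lists motor nerve injury, contour irregularity of a degree that would need surgery, and paradoxical hyperplasia, of which it says "Surgical intervention may be required".
- **Deadlines.** SAEs go to the sponsor within 24 hours (2.18, Time Period and Frequency; Reportable Incidents). Non-serious events related to the devices have 7 working days. Non-serious events related to KYBELLA have no deadline.
- **After the study.** The duty to report applies "if the investigator learns of any SAE, including a death, at any time after a participant has completed the final visit" and the event is judged reasonably related.
- **Drug rules.** Section 3.3.1 states "The investigator assumes all responsibilities per 21 CFR 812, 21 CFR 312, and other applicable regulations". Section 2.18, Serious Adverse Event Reporting Procedures, makes the sponsor responsible for "evaluating and reporting any serious adverse events and suspected unexpected serious adverse reactions". Neither place writes out seriousness criteria for a drug.
- **Endpoint.** Section 2.13.1 names seriousness, severity and duration as parts of the primary safety endpoint. Section 2.15.3.1 tabulates all adverse events by relationship, seriousness and severity.

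**The concern.** The trial gives a drug after a device, and the local harm both products share is motor nerve injury. Sites decide whether such an injury is serious from a list in which impairment counts only if it is permanent, or if someone intervenes to stop it becoming so. A facial weakness that lasts for months and then clears need not meet any item. The severity scale does not help, because an event can be rated incapacitating, hence severe, and still be non-serious.

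Seriousness decides how quickly the sponsor hears of the event and whether it enters the evaluation of unexpected serious drug reactions. It also decides which row the event occupies in the primary safety table, and whether an event learned of after the last visit has to be reported. If the criteria do not fit the expected harms, a report of no serious events says less than it seems to.

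**Working it through.** The point concerns a definition, so the plan has no figure to reproduce. The check applies the definition to the protocol's own example, follows the reporting routes, and then sizes the issue.

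**1. A nerve paresis that clears without treatment, against each criterion**

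| Criterion (2.18) | Met? |
|---|---|
| Death, life threat, fetal harm | No |
| Permanent impairment | No, since it resolves; undetermined while it is still open |
| Hospitalization | Only if the subject is admitted |
| Intervention to prevent permanent impairment | Only if one is made for that purpose |
| Prolonged reversible loss of function | No such criterion |
| Medically important event | No such criterion |

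Surgery for hyperplasia or contour irregularity corrects a change already present. Whether that counts as preventing permanent impairment is left to interpretation.

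**2. Routes open to a non-serious KYBELLA paresis**

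- 24-hour report: no, SAEs and unanticipated device effects only.
- 7 working days: no, device-related only. It would apply if the investigator also attributed the event to CoolSculpting.
- 1 working day under section 3.3.3: no, unanticipated device effects and life-threatening suspected reactions only.
- Withdrawal because of an event: reportable, but with no stated deadline.
- Safety Monitoring Considerations: 1 working day, if the investigator judges the event a potential risk to new subjects.

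Only the last is a rapid route, and it is discretionary.

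**3. Timing**

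- 298 / 30.44 = 9.8 months; 44 / 30.44 = 1.4 months.
- Last session to final visit: 12 ± 3 weeks = 63 to 105 days.
- First KYBELLA session to final visit: 63 to 105 days with one session. With the optional second session, 28 + 63 = 91 to 49 + 105 = 154 days.
- A 298-day paresis starting at the first session outlasts the final visit by 298 − 154 = 144 to 298 − 63 = 235 days. A median case, at 44 days, clears before it.
- Paradoxical hyperplasia may appear 2 to 5 months after treatment (6.2). With one KYBELLA session, the second CoolSculpting treatment can precede the final visit by as little as 35 + 63 = 98 days, or 98 / 30.44 = 3.2 months. Onset after the final visit is therefore possible, and the post-study rule then covers it only if it is an SAE.

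**4. Share of injuries still open at the final visit (assumed distribution)**

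Assume lognormal durations with median 44 days and 298 days as the 95th to 99th percentile.

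- σ = ln(298/44)/z = 1.913/2.326 = 0.822 (99th) to 1.913/1.645 = 1.163 (95th).
- P(T > 63) = 1 − Φ(ln(63/44)/σ) = 0.331 to 0.379.
- P(T > 105) = 1 − Φ(ln(105/44)/σ) = 0.145 to 0.227.

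So about 15% to 38% of injuries from the last session, if any occur, would still be open when permanence cannot be settled.

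**5. Expected numbers**

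The documents give no incidence for nerve injury, only its place among reactions seen in at least 2%. Taking 20 KYBELLA-treated subjects (the maximum), P(at least one) = 1 − (1 − p)^20:

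| Assumed p | P(at least one) | Expected injuries (20p) | Expected open at final visit (20p × 0.145 to 0.379) |
|---|---|---|---|
| 2% | 33% | 0.4 | 0.06 to 0.15 |
| 5% | 64% | 1.0 | 0.15 to 0.38 |
| 10% | 88% | 2.0 | 0.29 to 0.76 |

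The last column treats every injury as arising at the last session. One event in 20 is 1/20 = 5%.

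**The case against.** A reader might infer that a ten-month paresis is automatically non-serious and disappears from the safety results. The documents do not support that:

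- Permanence is one of several alternative criteria. Hospitalization or a preventive intervention would also make the event serious.
- No rule classes an unresolved injury as non-serious by default. The investigator must judge it.
- Section 2.15.3.1 tabulates every adverse event, so the paresis appears there as non-serious with its relationship and severity. Section 2.13.1 also lists duration.
- An injury that starts on study is already on the case report form. Section 2.18 requires follow-up of treatment-related events, serious or not, and of medically significant events until resolved or stable. SAE status is therefore not the only link after the final visit; the post-study gap concerns events that arise or come to light later.
- Ten months is the extreme of the range.

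All of this stands, and it limits the claim. It can also be said that drug rules enter by reference through 21 CFR 312 and the sponsor's duty on unexpected serious reactions, and that applying one named standard is a legitimate choice for a 20-subject feasibility study. That is fair as far as it goes. Sites, however, classify from the written list, and an event screened out there does not reach the sponsor as a serious reaction. The follow-up duties carry no reporting deadline, medically significant is not defined or tied to seriousness, and an already listed reaction may well not be judged a new risk to other subjects.

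**Conclusion.** The concern holds in limited form. One device-standard definition governs both products, and it has no criterion for persistent or significant but reversible loss of function or for a medically important event. On the protocol's own description, a KYBELLA nerve paresis of up to 298 days can be classed non-serious. If it is, and it is not also attributed to a device, no fixed reporting deadline applies and it stays out of the sponsor's serious-reaction evaluation. It is not lost from the record or from the safety table.

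The absolute effect is small: at an assumed incidence of 2% to 10%, roughly 0.06 to 0.76 injuries open at the final visit among 20 subjects. The 15% to 38% behind that figure is conditional on an injury occurring and on an assumed lognormal shape. The step from 0% to 5% is simply one event in 20. The case for change rests on the gap in the text, which needs none of these assumptions, and on prompt reporting of a harm listed for both products. The plan should be changed, but its efficacy analysis is unaffected.

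**What to change.** 1. In section 2.18, add two criteria to the SAE definition, for all adverse events regardless of cause: (f) persistent or significant incapacity or substantial disruption of normal function; (g) a medically important event in the investigator's judgment. Give prolonged motor nerve deficit and effects needing surgical correction as examples to consider. Do not tie them to the final visit, which can fall anywhere from day 63 to day 105 after the last session, or to relatedness, which would confound the table of relationship by seriousness.
2. Use the same definition for the seriousness rows in 2.15.3.1 and for the post-study rule in 2.18.
3. Extend the 7-working-day reporting to non-serious KYBELLA-related events.
4. Reconcile the SAE deadlines: 24 hours under Time Period and Frequency and Reportable Incidents, but 1 working day under Serious Adverse Event Reporting Procedures. Unanticipated device effects show the same split between Reportable Incidents and section 3.3.3.

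The cost is protocol and case report form wording, a few more SAE forms, and possibly a less favourable serious-event count. The Pregnancy paragraph already names further outcomes as SAEs, so study-specific additions fit the existing structure.

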### **Time Period and Frequency for Collecting AE and SAE Information**

All AEs and SAEs from the signing of the ICF until the last follow-up visit will be collected at the timepoints specified in the schedule of activities, and as observed or reported spontaneously by study participants.

Medical occurrences that begin after signing of informed consent and before administration of study treatment will be recorded as an AE on the appropriate CRF.

All SAEs will be recorded and reported to the sponsor or designee within 24 hours of learning about the report. All non-serious AEs related to the devices used in the study, as well as Device Complaints, will be reported to the sponsor within 7 working days. The investigator will submit any updates on these events to the sponsor within 24 hours of it being available.

Investigators are not obligated to actively seek AE or SAE in former study participants. However, if the investigator learns of any SAE, including a death, at any time after a participant has completed the final visit of the study, and he/she considers the event to be reasonably related to the study treatment or study participation, the investigator must promptly report the event to the sponsor.

